Older obese adults suffer disproportionately from walking mobility limitations. Sedentary, obese older adults are at an increased risk for having or developing difficulties with mobility. These individuals are often excluded from studies due to their advanced mobility limitations. A number of studies have compared the effects of weight loss alone, exercise alone, or weight loss in combination with exercise on functional performance in older adults, but none of the studies have specifically targeted subjects who use walking assistive devices. The purpose of this study is to test the effects of a 3 month multi-modal balance intervention (MMBI) with a nutrition program with optional retention till 24 months on fitness, functional performance, mobility, and muscle mass. The results of this study will lead to new and more effective interventions that could reduce disability, fall risk, injury-related hospitalization and death in older Veterans.

ID: VIEW4E02805CF7000
Name: v2_Lay Summary

Justification, Objective, & Research Design

If you uploaded a separate research protocol document in the 'Research Protocol' page, cite the applicable section and page numbers from that document in the answer boxes below.

- 1 *** Describe the purpose, specific aims, or objectives of this research. State the hypothesis to be tested:**
 Specific aim 1: Examine the effects nutrition + multimodal balance intervention (MMBI) on mobility and functional performance in the following outcomes:
 a. 6 minute walk (primary outcome)
 b. Other physical performance outcomes: 6MW with economy of gait, gait rite, four square step test, 8 foot up and go, short physical performance battery, grip strength, lower extremity strength
 Specific aim 2: Examine the relationship between muscle mass, strength, and functional performance using DXA and CT scans to quantify body composition.
 Specific aim 3: Examine the impact of the intervention on patient reported measures of function and disability using the Late Life Function and Disability Instrument (LLFDI).
- 2 *** Discuss the research design including but not limited to such issues as: probability of group assignment, potential for subject to be randomized to placebo group, use of control subjects, etc.:**
 All subjects will now receive MMBI and nutrition (combined intervention). Weight loss will be a covariate in the analyses.
- 3 *** Describe the relevant prior experience and gaps in current knowledge. Describe any relevant preliminary data:**

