HYPOCALORIC NUTRITION INTERVENTION: Subjects will attend nutrition sessions once a week for the first 3 months. The nutrition classes will be lead by registered dietitians, either in person, via phone or via telehealth. During phase 2, subjects will complete three 24 hour food records that will be reviewed by the study dietitian and analyzed using Nutritionist Pro software. If necessary the study dietitians will communicate via phone with participants to collect this information. This will provide an assessment of nutritional adequacy at baseline to rule out the risk of nutritional deficiencies. One on one counseling will be provided. Three 24 hour food records is considered the gold standard and is necessary to provide the study dietitian with the information necessary to make a thorough dietary assessment. The ASA24 system (<https://asa24.nci.nih.gov/>) will be used to collect 3 24 hour food recalls during baseline for both groups, and then at 3 months. Extensive evidence has shown that 24-hour dietary recalls provide the best quality, least biased dietary data as compared to paper-based food diaries. National Cancer Institute (NCI) investigators created the free, web-based Automated Self-Administered 24 hour Recall (ASA24) system to administered 24-hour recalls. The ASA24 system was developed with Westat®, and builds on the Food Intake Recording Software System (FIRSSt) developed by [name] of the Baylor College of Medicine. The ASA24 system consists of a Respondent Website, used to collect data from participants, and a Researcher Website for managing study logistics and access nutrient and food group data files. The coordinator or study dietitian will log into the VA computer and access the website and subject specific food logs. The computer will be logged on just prior to the subject coming into the room, coordinator will navigate to the website, place subject in front of the screen, and provide the subject with instructions. Coordinator will remain with subject at all times, and then will close out the computer. At no time will the subject have access to navigate elsewhere on the computer or be left alone. There is no identifying data for participants on the ASA24 website as they are specified a unique numeric identifier for each Respondent and download system-generated usernames and encrypted passwords that they provide to Respondents so that they may access the application. Only the study's investigator(s) and the ASA24 operations team can access response data. Access is gained through usernames and strong passwords. Data output is in SAS files, which will be stored on the VA computer study folder in the GRECC file I:\shared\all\MMBI and Weight Loss Merit and behind password lock. Response data are secured at the hosting site using industry standard security controls, including firewalls and encryption. All data entered into the ASA24 system at the Respondent's computer is encrypted by the internet browser (e.g., Internet Explorer, Firefox) before they are transmitted to our servers using Secure Socket Layer (SSL) Technology. SSL allows for the authentication of the sending and receiving computers.

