SAMPLE SIZE CALCULATIONS were determined for the physical outcomes. Perera and colleagues proposed that an improvement of 19-22 meters on the 6 minute walk test (6MWD) would be clinically meaningful and an increase of 47-49 meters would be considered substantial (72). In our prior studies in subjects with impaired mobility, exercise increased 6MWD 10 to 30%. In our preliminary studies in obese mobility limited Veterans enrolled in Gerofit, the 6MWD increased by 15% (57 +/- 60 m) and the number of chair stands performed by 19%. We anticipate greater improvements with weight loss + MMBI on the order of 30 to 50 M greater improvement in MMBI + weight loss versus MMBI only. Using lower estimates, if the true difference in mean response of matched pairs is 30 +/- 50 meters, we will need to study 45 subjects in each group to be able to reject the null hypothesis with two-sided power of 0.8 and Type I error probability of 0.05. We previously reported that an exercise intervention in middle aged and older overweight and obese men increased VO2peak (L/min) by 17% with no change with weight loss (50). The study by Villareal et al. reported a 17% improvement in VO2peak in the combined group versus about 6% in the diet group. To detect a 15% difference in VO2peak between groups with a power of 0.80 and a p-value <0.05, we would need to enroll 41 subjects per group, which is close to the sample size required for the 6MWD. On a percentage basis we anticipate that there will be even more substantial improvements in lateral mobility and balance as assessed by the four square step test (FSST) than that observed for the change in usual gait speed or 6MWD. In our preliminary data, the MMBI decreased the time to complete the FSST by 24%, with the greatest improvement in the frailest subjects. Therefore, fewer subjects might be required to demonstrate a difference in the improvement in balance between groups.

We will enroll 60 subjects. Typical attrition rates are 20-25%, primarily due to the development of non-study related medical problems. This will result in 45 completers. If a greater than anticipated number of subjects fail to complete the study, we will enroll additional subjects.

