2 * Provide the plan for data analysis. Include in the description the types of comparisons that are planned (e.g., comparison of means, comparison of proportions, regressions, analysis of variance, etc.), which is the primary comparison/analysis, and how the analyses proposed will relate to the primary purposes of the study:

All comparisons of primary and secondary outcomes will be performed in accordance with intention-to-treat principles. As with all clinical trials, it is anticipated that there may be missing data elements. Multiple imputation will be used to account for missing values. Our first analyses will be exploratory designed to identify extreme values. Extreme values will be checked to make sure they are not the result of data entry errors. Statistical significant will be a two-sided alpha of 0.05.

Specific aim 1. Our study will compare the effects of MMBI+nutrition on mobility and functional performance in older obese Veterans with walking impairment requiring a walking assistive device. We will use repeated measures ANOVA to model the time-course of our outcome measures. We will use AICC (a modification of Akaike's Information Criterion) to choose between three covariance structures that can account for the serial auto-correlation of our subject's data.

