 Opt In Out PostCard RISE 09242019.pub(0.02)	9/16/2019 3:48 PM	9/24/2019 10:32 AM
 VINCI RISE Recruitment Letter 09242019.doc(0.02)	9/16/2019 3:48 PM	9/24/2019 10:32 AM
 Invitation letter(0.04)	4/27/2016 9:31 AM	11/8/2018 12:58 PM
 Phone screen(0.01)	4/27/2016 9:16 AM	4/27/2016 9:16 AM

Advertising

1 * Will you be using advertisements to recruit potential participants?

Yes No

ID: VIEW4E0BCCF811000
Name: v2_Advertising

Advertising Detail

You indicated that you will be using advertisements to recruit potential participants.

1.1 *Select the mode(s) of advertising (check all that apply):

- Radio
- Internet
- Print
- Television
- Other

1.1.1 If Other, specify:

1.2 *Provide exact text of all proposed advertisement(s):

TEAR OFF NUMBER FLYER

DO YOU HAVE A SLOW WALKING SPEED?

DO YOU USE AN ASSISTIVE DEVICE TO WALK?

Participants are needed for a study to determine the impact of 3 months of exercise versus exercise and weight loss on fitness and body composition in patients who are overweight.

WHO MAY BE ELIGIBLE?

Men and women 60 years and older

Walk with a walking aid (cane or walker) OR have problems walking

Are a Veteran

Need to lose weight

For more information about this research study please contact: [contact] [name]

BROCHURE

MULTI-MODAL EXERCISE & WEIGHT LOSS IN OLDER VETERANS WITH LIMITED MOBILITY

An information guide for providers and potential study participants about this VA funded, IRB-approved study

University of Maryland School of Medicine

VA Maryland Health Care System

Geriatric Research, Education & Clinical Center

ABOUT THE STUDY

- About 1/3 of older Veterans are obese and obesity is a risk factor for mobility problems in older adults
- Using a walking aid can alter normal walking patterns and cause walking to be harder and more tiring, leading to mobility limitations
- Exercise training and weight loss may lead to improvements in mobility
- This study evaluates the impact of 3 months of exercise training & weight loss on fitness, functional performance, and body composition

WHO IS ELIGIBLE

- Are a Veteran
- Age 60 and older
- Walk with a walking aid (cane, walker) OR have difficulty walking around
- Need to lose weight ($BMI \geq 30 \text{ kg/m}^2$)
- Do not have a lower limb amputation

WHAT DO YOU HAVE TO DO?

- Medical history and physical exam
- Aerobic fitness assessments
- Strength and balance tests

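### The 80% power and 45 per group belong to a two-arm comparison that the single-arm trial cannot make; no power is given for the change it will estimate

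*Combined protocol and SAP*

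**What the plan says.** **Design.** Justification, Objective, & Research Design, item 2, states: "All subjects will now receive MMBI and nutrition (combined intervention". Weight loss is to be a covariate. The aims in item 1 concern the effect of the combined intervention and state no comparison.

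**Analysis.** Sample Size and Data Analysis, item 2, Specific aim 1: "We will use repeated measures ANOVA to model the time-course of our outcome measures". No comparator or group term is described.

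**Sample size.** Item 1 of the same section expects an effect "on the order of 30 to 50 M greater improvement in MMBI + weight loss versus MMBI only". It takes the lower end: if "the true difference in mean response of matched pairs is 30 +/- 50 meters, we will need to study 45 subjects in each group", at 80% power and two-sided 0.05. It adds 41 per group for a between-group difference in VO2peak, and suggests that fewer subjects may be enough to "demonstrate a difference in the improvement in balance between groups". It then enrols 60 in total at 20-25% attrition: "This will result in 45 completers".

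**Other two-arm wording.** The nutrition section of Study Procedures collects food recalls "during baseline for both groups". The tear-off flyer advertises "3 months of exercise versus exercise and weight loss on fitness and body composition". Potential Benefits and Alternatives, item 2, still hypothesises larger gains with nutrition plus MMBI than with MMBI only.

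**The concern.** The only quantitative justification for the primary outcome, six-minute walk distance (6MWD), describes a contrast between two treatments, and the trial now has one treatment. The figure of 45 also changes meaning within the paragraph. It starts as the number in each of two groups and ends as the number of completers in the whole trial. A reader who sees 45 twice will assume that 80% power for 30 m carries over. It does not.

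Two things are at stake. First, the plan does not tell the reader what 6MWD change 45 completers can detect, or how precisely that change will be estimated. Second, the leftover comparative wording suggests that the added effect of weight loss can be tested. Without an MMBI-only arm, change over time cannot be attributed to it.

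**Working it through.** **Inputs from Sample Size and Data Analysis, item 1:** difference 30 m; 50 m taken as an SD; two-sided alpha 0.05; power 0.80; 60 enrolled; attrition 20-25%; 45 completers; preliminary 6MWD change 57 +/- 60 m; 19-22 m called clinically meaningful.

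**Step 1. Reproduce the plan's 45.** The standardised difference is 30/50 = 0.6. For two independent groups the normal approximation is n = 2(1.960 + 0.842)²/0.6² = 43.6, so 44 per group. The noncentral t calculation gives 44.6, so **45 per group**, with 80.4% power at 45. The plan's number is correct arithmetic for two independent groups.

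**Step 2. Test the matched-pairs label.** Taking 50 m as the SD of the paired differences, n = (1.960 + 0.842)²/0.6² = 21.8 by the normal approximation and 23.8 by noncentral t, so **24**.

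**Step 3. What the two-arm claim would require.** 2 × 45 = 90 completers. Enrolment would be 90/0.80 = 112.5, so 113, or 90/0.75 = 120. The plan has 60 enrolled: 60 × 0.75 = 45 completers, or 60 × 0.80 = 48.

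**Step 4. What the current design can do.** Assumptions:
- the contrast is change from baseline to 3 months, since the aims name no primary time point;
- a paired t-test approximates the repeated measures contrast;
- the SD of change is 50 m (borrowed from the old between-arm contrast) or 60 m (the preliminary figure, read as an SD).

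The 95% confidence interval half-width is t(0.975, n − 1) × SD/√n. With n = 45, t = 2.015, giving 2.015 × 50/√45 = 15.0 m and 2.015 × 60/√45 = 18.0 m. By noncentral t, 80% power at n = 45 is reached at 0.427 SD.

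| 45 completers | SD 50 m | SD 60 m |
|---|---|---|
| Change detectable at 80% power | 21.4 m | 25.6 m |
| 95% CI half-width | 15.0 m | 18.0 m |
| Power for 19 m | 70.3% | 54.7% |
| Power for 22 m | 82.3% | 67.2% |
| Power for 30 m | 97.6% | 90.7% |

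With 48 completers the detectable changes are 20.6 m and 24.8 m.

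**Step 5. VO2peak.** The 41 per group cannot be checked because no SD is given. It is in any case a between-group number.

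**The case against.** **The trial is probably large enough, and the arithmetic of 45 is right.** Both parts stand. Power for 30 m is 91-98%. For a change as large as the preliminary 57 m it exceeds 99.9%, although that cohort did GeroFit, not this intervention. The fault is in the contrast and the label. It still leaves the actual primary analysis with no power or precision statement.

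**The figure of 24 depends on how 50 m is read.** True. If 50 m is each pair member's SD and the within-pair correlation is zero, the SD of differences is 50√2 = 70.7 m and 46 pairs are needed. But then the pairing does nothing, and the 30 m is still a between-arm difference.

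**The plan deals with weight loss as a covariate.** Adjustment within one treated group does not create a control arm, so it does not restore the comparison.

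**Other comparators may exist.** Prospective Data mentions sharing data with another protocol to compare populations, and pre-pandemic enrollees may return. No comparison with an MMBI-only group is described from either source. It is still safer to write that there is no concurrent comparison group.

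**Intention-to-treat with multiple imputation could bring up to 60 into the analysis.** This stands as a limit on the figures. With full information on 60, the detectable changes would be 18.4 m (SD 50 m) and 22.1 m (SD 60 m). Imputation cannot recover all of that, so 45, the plan's own completer count, is the conservative basis.

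**Conclusion.** The concern holds, and the paragraph must be corrected. That the stated power belongs to another design follows from the documents alone: one treatment for all, a time-course analysis, and a sample size for two groups. The shortfall against the old claim is 45 completers planned against 90 required, but the trial no longer makes that claim. That 45 is not a matched-pairs number rests on reading 50 m as the SD of the differences, which is the plain reading.

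This is not evidence that the trial is too small. Power is high for 30 m but only 55-82% across the 19-22 m that the plan calls clinically meaningful. Those figures rest on the assumed SDs of 50-60 m, 45 completers, a 3-month contrast and the paired approximation.

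**What to change.** Replace the sample-size paragraph with power and precision for within-person 6MWD change at a named time point. For example:

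> All participants receive the combined intervention and there is no concurrent comparison group. With 45 completers and two-sided alpha 0.05, approximating the repeated measures contrast from baseline to 3 months by a paired t-test, the study has 80% power for a mean 6MWD change of 21.4 m if the SD of change is 50 m (95% CI half-width 15 m), or 25.6 m if it is 60 m (18 m). Both SDs are assumptions. Uncontrolled change cannot be attributed to the added weight loss, and adjusting for weight loss as a covariate does not alter this.

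Remove the matched-pairs, per-group, between-group and MMBI-only wording from that paragraph, and the two-arm wording from the nutrition section and the flyer. Restate the hypothesis in Potential Benefits and Alternatives as within-person change.

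Three related points need reconciling; the documents do not settle them:
- **VO2peak.** It has a sample-size calculation but is not in the outcome lists in the aims or Study Procedures, although fitness is still named in the lay summary, Specific aim 2 and the advertisements.
- **Preliminary 6MWD gain.** It is 57 m in the sample-size section. The preliminary data give 418 − 363 = 55 yards, or 55 × 0.9144 = 50.3 m. State whether these are the same cohort.
- **Enrolment.** It is 60 in the sample-size section and 240 in Participant Selection, where enrolment means signed consent. State whether 240 includes screen failures, pre-pandemic enrollees or repeat consents.

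The cost is wording only: no extra patients, visits or analyses.

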 The order of the tests will vary from subject to subject depending upon their schedule and the availability of the equipment.

After completion of baseline testing, participants will enter the intervention phase

Phases 3-5. Interventions and Outcome Assessments will be performed at 3 months and at 6, 12 months and a final assessment at the end of 24 months for subjects who are in the optional retention exercise program.

INTERVENTIONS

MULTIMODAL BALANCE INTERVENTION (MMBI): The MMBI has been designed to specifically address the proximal strength, balance, and mobility deficits of these severely deconditioned older obese Veterans who use assistive devices. The MMBI intervention will be conducted in the VA hospital or the VA Annex in downtown Baltimore and at the more suburban Loch Raven Community Based Outpatient Clinic. The two sites are 6 miles apart and there is routine shuttle service between them. Our MMBI will be held once a week or once every other week for an hour and will consist of a dynamic balance class (30 minutes), a supervised obstacle course (10 minutes), and lower extremity and core strengthening (20 minutes). The exercises will focus on dynamic weight shifts with an emphasis on the lateral and diagonal directions. Over time the exercises will gradually increase in difficulty. An instructor will lead each class and 1-2 assistants will be present to assist in mitigating the risk of falls. The supervised obstacle course will focus on obstacle negotiation, walking over challenging surfaces, and moving in the lateral, diagonal, and backward directions. Strength training of the lower extremities and core will focus on strengthening the major muscles of the lower extremity and core (hip flexors/extensors, hip abductors/adductors, knee flexor/extensors, ankle planter flexor/dorsiflexors, ankle invertors/evertors, and core abdominal/back extensor muscles) utilizing commonly standard gymnasium equipment, ankle weights, and body weight. If group exercise is unavailable due to COVID-19, individuals will be provided with a written home exercise program to perform or sessions via telehealth twice a week. The intervention is 3 months long with optional extension out to two years.

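### The plan names no primary visit or contrast for 6-minute walk distance; with visits after 3 months apparently limited to an optional extension and weight loss as a covariate, an intention-to-treat reading of the time-course is not secured

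*Combined protocol and SAP*

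**What the plan says.** All places are in the combined protocol and SAP.

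- **Primary outcome.** Justification, Objective, & Research Design (item 1) and Study Procedures (outcome measures) name 6-minute walk distance (6MWD). Neither attaches a visit to it.
- **Analysis.** Sample Size and Data Analysis, item 2, asks the investigator to say "which is the primary comparison/analysis, and how the analyses proposed will relate to the primary purposes of the study". For Aim 1 the answer is "We will use repeated measures ANOVA to model the time-course of our outcome measures", and "We will use AICC (a modification of Akaike's Information Criterion) to choose between three covariance structures". The three structures are not named.
- **Analysis principle and missing data.** The same item says "All comparisons of primary and secondary outcomes will be performed in accordance with intention-to-treat principles" and "Multiple imputation will be used to account for missing values". It gives no imputation model and does not say which visits are covered.
- **Covariate.** The research design answer states: "Weight loss will be a covariate in the analyses".
- **Later visits.** The Lay Summary describes a 3-month programme "with a nutrition program with optional retention till 24 months". Study Procedures, Phases 3-5, lists assessment at 3 months and then "6, 12 months and a final assessment at the end of 24 months for subjects who are in the optional retention exercise program". The outcome-measures paragraph ties months 6 and 12 to people in the longer intervention, in a sentence with a word missing, and does not list month 24.
- **Places without that limit.** The duration answer (Study Procedures, item 3) expects about 24 months from people who complete everything. The Aim 2 analysis lists scans at baseline, 3, 6, 12 and 24 months. The payment schedule lists payments at 6, 12 and 24 months.
- **Aim 3.** The analysis of the patient-reported instrument follows the Aim 1 plan.

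**The concern.** A time-course model with four post-baseline visits can yield an overall time test, four change-from-baseline contrasts and various averages. Nothing in the plan says which one decides the trial.

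The choice matters because the visits may not represent the same people. If attendance after 3 months depends on choosing an extension, those visits describe a self-selected group, yet the plan would report all comparisons as intention-to-treat.

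The weight-loss covariate adds a second ambiguity. It is measured after baseline and is a target of the programme, and the plan does not say how it enters the model. Entered uncentred, it makes the time effect the change expected at zero weight loss, which removes any benefit that comes through losing weight. Centred at its mean, it would leave a single-visit change in a linear model roughly intact. The documents do not say which is meant.

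**Working it through.** **1. Does the sample-size section supply the missing contrast?** Inputs from Sample Size and Data Analysis, item 1: difference 30 m, SD 50 m, two-sided alpha 0.05, power 0.80, 45 per group.

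- Normal approximation: 2 x (1.960 + 0.842)² x (50/30)² = 43.6, so 44 per group. The two-sample t calculation gives 44.6, so 45. The stated figure is reproduced.
- 60 enrolled x (1 - 0.25) = 45 completers, also as stated.

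This is a comparison of exercise plus weight loss with exercise alone. The current design gives everyone both components, and the calculation names no visit, so it cannot fill the gap.

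**2. What leaving the contrast open allows.** If each of the four post-baseline visits were tested at 0.05, the chance of at least one false positive would be 1 - 0.95⁴ = 18.5% under independence, and less with positively correlated visits.

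**3. What one contrast would deliver.** For a within-person change in 45 people (one-sample t, two-sided 0.05), power for a 30 m change is about 98% with SD 50 m and about 91% with the pilot SD of 60 m. The change detectable with 80% power is 21.4 m or 25.6 m respectively.

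**4. What happens at later visits if only entrants are assessed.** Let u be the share of 3-month completers who enter, E the entrants' mean gain at a later visit, and D the decliners'. For simplicity, take entry as unrelated to earlier walk distance.

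- True mean gain for everyone: u x E + (1 - u) x D.
- An imputation model, or a likelihood fit over all participants, learns the later visit only from entrants and so returns about E. Choosing covariance structures by AICC implies a likelihood fit, so dropping imputation does not avoid this.
- Error: E - [u x E + (1 - u) x D] = **(1 - u) x (E - D)**.

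**5. Illustration only.** u, E and D are all assumed. The 3-month gain is taken as 50.3 m, from the GeroFit preliminary data: (418 - 363) yards x 0.9144.

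| Share of gain kept: entrants / decliners | u = 30% | u = 50% | u = 70% |
|---|---|---|---|
| Equal | 0 m | 0 m | 0 m |
| 80% / 50% | 10.6 m | 7.5 m | 4.5 m |
| 100% / 50% | 17.6 m | 12.6 m | 7.5 m |

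For example, 0.5 x (0.80 - 0.50) x 50.3 = 7.5 m. If decliners did better than entrants (50% / 80%), the sign reverses: -7.5 m at u = 50%.

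A simulation checked the likelihood claim. It used 4,000 cohorts of 60 per setting, baseline mean 332 m and SD 108 m, change SD 60 m, 25% lost before month 3, random entry and later noise SD 20 m. For u = 50% and 80% / 50% it gave 7.7 m. The estimated 3-month gain stayed between 50.0 and 50.5 m across the settings run. This confirms the mechanism. It says nothing about the real values of u, E and D.

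**6. How much later data could be unobserved.** With 60 enrolled, 25% missing at 3 months and an assumed 50% uptake, 60 x 0.75 x 0.50 = 22.5 people are seen at each later visit. That leaves 62.5% unobserved. At 100% uptake the figure is 25%.

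**The case against.** **Three months is obvious.** The Lay Summary, the intervention description and the brochure all describe a 3-month programme. That makes month 3 the natural reading, but none of them is an analysis rule. Other text points elsewhere: the nutrition section sets its weight-loss target over the first 6 months, and the preliminary-data section says the exercise intervention will last longer than 3 months of GeroFit. The plan's author has to reconcile these.

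**A visit that was never due is not a missing value.** This is fair. A reader might infer that the plan will impute visits nobody was scheduled to attend. It does not say so; it only fails to exclude it. The point survives without that reading, because a likelihood fit over everyone has the same effect.

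**The later visits may be for everyone.** This is also open. In Phases 3-5 the limit may attach only to month 24, and three other sections omit it. The concern about later means is therefore conditional.

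**The gains may persist.** The preliminary balance study reports improvements maintained after a four-month home programme. Those people had a history of falls, were not selected for obesity and kept exercising, so they do not show what decliners would do. Recruitment draws partly on existing exercise and weight-management programmes, so declining the extension need not mean stopping. A reader might infer that later results would be overstated by a clinically important distance, given the 19-22 m meaningful change cited in the sample-size section. The documents do not support that: the inputs are unknown, and the error can be zero or negative.

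**No harm to a primary result is shown.** Correct for month 3, which the extension does not bias. The gap is that the plan does not make month 3 the result to be judged.

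**Conclusion.** The point holds in a limited form. No section names a primary visit or contrast for 6MWD, although the form asks for one and the sample-size calculation cannot supply it. The role of the weight-loss covariate is undefined, so what the primary model estimates is unclear.

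If only extension entrants are assessed after 3 months, means at months 6 to 24 and any overall time test from an all-participant model or imputation would not be intention-to-treat. Their error would be (1 - uptake) x (entrants' minus decliners' later gain). Its size and direction cannot be derived from the documents, and the metre figures above only illustrate the formula. The 3-month estimate is not affected by this mechanism. Aim 3 inherits the same gap.

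This should be corrected. Confidence is medium, because the schedule text is itself unsettled.

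**What to change.** In Sample Size and Data Analysis, item 2:

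1. Name one primary contrast with one degree of freedom. The baseline-to-3-month change in 6MWD is the natural choice, because everyone receives a 3-month intervention. First reconcile it with the 6-month weight-loss target and the statement on longer duration. It can be estimated within the planned repeated-measures model; a model using only the two visits is optional.
2. Define the analysis set. State which baseline and 3-month values count for participants invited back after the COVID-19 pause (Study Procedures, Phase 1; Informed Consent Process).
3. Do not adjust the primary contrast for weight loss. Make any weight-loss-adjusted analysis secondary and explanatory.
4. State that visits not due are not missing and are not imputed.
5. Reconcile Phases 3-5, the outcome-measures paragraph, the duration answer, the Aim 2 visit list and the payment schedule on who is assessed after 3 months.
   - If only entrants are assessed, report months 6, 12 and 24 for entrants only, labelled a self-selected subgroup. Give the numbers entering and observed at each visit, and show their 3-month 6MWD beside that of non-entrants.
   - If everyone is assessed, say so and put extension status in the imputation model.
6. Apply the same rule to Aim 3.

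The cost is plan wording and one clarification of the visit schedule. The downside is that, if only entrants are assessed, no intention-to-treat claim can be made beyond 3 months.
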